15.3. Subject Characteristics

15.3.1. Demographics

The demographic information will be summarized for each analysis population by treatment group.

15.3.2. Medical and Surgical History

Prior medical conditions or procedures will be summarized by body system and treatment group.

15.3.3. Prior and Concomitant Medications

Prior and concomitant medications will be coded according to the WHO Drug Dictionary. The incidence (number and percent) of prior and concomitant medication use will be summarized by treatment group.

15.3.4. Subject Disposition and Exposure to Investigational Medicinal Product

Subject disposition and treatment exposure will be summarized. The number of subjects who complete the study and who do not complete the study along with the reasons for discontinuation from the study will be summarized.

15.4. Safety Analysis

All subjects who receive at least 1 dose of IMP will be included in the safety analyses.

15.4.1. Adverse Events

The MedDRA coding terms will be used for coding AEs. The number of AEs and the number of subjects reporting AEs will be listed and summarized descriptively by body system, preferred term, severity, and causality for each treatment group. Only TEAEs (events that are new in onset or aggravated in severity following treatment), will be included in all summaries. SAEs and deaths will be summarized.

15.4.2. Clinical Laboratory Tests

Clinical laboratory test results will be summarized descriptively and presented in data listings.

15.4.3. Physical Examination Findings

All physical examination results will be summarized descriptively and presented in a data listing.

15.4.4. Electrocardiogram Findings

Electrocardiogram measured changes from baseline for sinus rhythm, heart rate, PR interval, RR interval, QRS duration, Q-T Interval, and QTcB will be summarized.

15.4.5. Vital Signs

Vital sign results (heart rate, diastolic/systolic blood pressures, respiratory rate and weight) and corresponding changes from baseline values will be summarized at each visit with descriptive statistics by treatment group.

15.5. Efficacy Analysis

Efficacy analyses will be performed on the mITT Population. All efficacy endpoints will be summarized and analyzed. Pearson's chi-squared test will be used to evaluate the treatment difference between treatment groups for the categorical response endpoints. The continuous response endpoints will be analyzed using 2-sample t-test. The time-to-event endpoints will be analyzed using log-rank test. Kaplan-Meier curves will also be presented.

Additional exploratory analyses will be performed as appropriate. Such analyses may include logistic regression model, analysis of variance model, and/or mixed-effects model. Subgroup analyses based on demographics, baseline characteristics, study compliance, etc, will also be performed.

Missing data imputations will be performed as appropriate. In general, the last-observation-carried-forward method will be used to impute missing data. Additional missing data imputation may be performed as needed.

15.6. Interim Analysis

No interim analysis of the data is planned.

15.7. Statistical Power and Sample Size Considerations

Formal sample size calculations were not performed. The sample size is based on recent literature of comparative studies ([Gibson et al., 1996](#); [Baughman et al., 2006](#); [Judson, 2014](#)) in sarcoidosis.

15.8. Deviations from Statistical Analysis Plan

Any deviations from the planned statistical analysis will be described and justified in the final clinical study report as appropriate.

16. ADVERSE EVENTS AND SERIOUS ADVERSE EVENTS

16.1. Safety

For safety information about Acthar Gel, refer to the most recent version of the Package Insert ([Mallinckrodt ARD LLC, 2019](#)).

16.2. Definitions

AE

An AE is any untoward or undesirable medical occurrence in a subject who is administered an IMP, which does not necessarily have to have a causal relationship with this treatment. Examples of AEs include but are not limited to:

- Clinically significant laboratory findings.
- Clinically significant changes in physical examination findings.
- An AE occurring due to IMP overdose whether accidental or intentional.
- An AE occurring from investigational medicinal abuse.
- An AE associated with investigational medicinal withdrawal.
- Unexpected AE.

An unexpected AE is defined as an AE, the nature and severity of which is not consistent with the applicable product information in the most recent version of the package insert ([Mallinckrodt ARD LLC, 2019](#)).

Adverse experiences (serious or non-serious) that commonly occur in the study population or background regimen will be considered anticipated events. Such events include known consequences of the underlying disease (disease-related) or condition under investigation (eg, symptoms, disease progression) and events unlikely to be related to the underlying disease or condition under investigation but common in the study population independent of drug therapy. Anticipated events, when reported, to be associated with the use of the investigational product, are a subset of unexpected AEs (events not listed in the package insert [[Mallinckrodt ARD LLC, 2019](#)]). However, these events do not warrant expedited reporting as individual cases when serious criteria have been met because it is not possible to determine that there is a reasonable possibility that the drug caused the event. As a result, they do not meet the definition of a suspected adverse reaction.

SAE

An SAE is defined as any untoward medical occurrence that at any dose results in any of the following outcomes:

- Death.
- A life-threatening AE.
- Inpatient hospitalization or prolongation of existing hospitalization.
- A persistent or significant incapacity or substantial disruption of the ability to conduct normal life functions.

- Results in a congenital anomaly/birth defect.

Important medical events that may not result in death, be life-threatening, or require hospitalization may be considered serious when, based upon appropriate medical judgment, may jeopardize the subject and may require medical or surgical intervention to prevent one of the outcomes listed above. Examples of such medical events include allergic bronchospasm requiring intensive treatment in an emergency department or at home, blood dyscrasias or convulsions that do not result in inpatient hospitalization, or the development of drug dependency or drug abuse.

Death

Death is an outcome of an event. The event that resulted in death should be recorded and reported on the SAE Form. All causes of death must be reported as SAEs. The investigator should make every effort to obtain and send death certificates and autopsy reports (if applicable) to Mallinckrodt.

Life-Threatening Event

A life-threatening event refers to immediate risk of death as the event occurred per the reporter. A life-threatening event does not include an event that, had it occurred in a more severe form, might have caused death but, as it actually occurred, did not create an immediate risk of death. For example, hepatitis that resolved without evidence of hepatic failure would not be considered life-threatening, even though hepatitis of a more severe nature can be fatal. Similarly, an allergic reaction resulting in angioedema of the face would not be life-threatening, even though angioedema of the larynx, allergic bronchospasm, or anaphylaxis can be fatal.

Hospitalization

Hospitalization is defined as an official admission to a hospital. Hospitalization or prolongation of a hospitalization constitutes a criterion for an AE to be serious; however, it is not in itself considered an SAE. In absence of an AE, a hospitalization or prolongation of a hospitalization should not be reported by the investigator as an SAE. Such situations include, but are not limited to, the following:

- A hospitalization or prolongation of hospitalization is needed for a procedure required by the protocol.
- A hospitalization or prolongation of hospitalization is part of a routine procedure followed by the center (eg, stent removal after surgery). This should be recorded in the study file.
- A hospitalization for a preexisting condition that has not worsened.
- Note that the following hospitalizations are not considered SAEs in Mallinckrodt clinical studies:
 - A visit to the emergency department or other hospital department of less than 24 hours that does not result in admission (unless considered "important medical event" or life-threatening event).

16.3. Adverse Event and Serious Adverse Event Classifications

Investigational Medicinal Product Relatedness

The following classifications should be used when evaluating the relationship of AEs or SAEs to study treatment ([Table 3](#)).

Table 3: AE Relationships

Relationship	Definition
Not Related	No relationship between the experience and the administration of study treatment; related to other etiologies such as concomitant medications or subject's clinical state.
Unlikely Related	The current state of knowledge indicates that a relationship is unlikely.
Possibly Related	A reaction that follows a plausible temporal sequence from administration of the study treatment and follows a known response pattern to the suspected study treatment. The reaction might have been produced by the subject's clinical state or other modes of therapy administered to the subject.
Related	A reaction that follows a plausible temporal sequence from administration of the study treatment and follows a known response pattern to the suspected study treatment and can be confirmed with a positive re-challenge test or supporting laboratory data.

Severity Assessment

For purposes of consistency, if required, the investigator may use the intensity grades presented in [Table 4](#).

Table 4: AE Severity Grades

Grade	Definition
Mild	Does not interfere with subject's usual function and activities
Moderate	Interferes to some extent with subject's usual function and activities
Severe	Interferes significantly with subject's usual function and activities

If an AE increases in severity (eg, from moderate to severe); decreases in severity (eg, changes from moderate to mild); or there is a change in seriousness, a new AE will be opened and the original AE will be closed. If an AE is still ongoing at the time of a subject's completion of the final visit, the resolution/stop date and time is left blank.

To ensure there is no confusion or misunderstanding of the difference between the terms "serious" and "severe," which are not synonymous, the following note of clarification is provided:

The term "severe" is used to describe the intensity (severity) of a specific event (as in mild, moderate, or severe myocardial infarction); the event itself, however, may be of relatively minor medical importance (such as a severe headache). This is not the same as "serious,"

which is based on the subject/event outcome or action criteria usually associated with events that pose a threat to a subject's life or functioning. Seriousness (not severity) serves as a guide for defining regulatory reporting obligations.

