16.4. Adverse Event and Serious Adverse Event Recording and Reporting

AEs and SAEs will be recorded from signing of the ICF through completion of the follow-up visit, which will take place 4 weeks (\pm 2 days) after the subject has received the last administration of IMP. The investigator is required to record the AE or SAE regardless of the severity of the event or its relationship to study treatment. The investigator must follow up on all AEs and SAEs until the event has resolved or stabilized or at such time the investigator refers the subject to a nonstudy physician. The investigator will document the further follow-up information in the subject's source document.

During the period specified above, the investigator will:

Record all AEs and SAEs in the source documents from the signing of the ICF through the completion of the follow-up telephone call.

Record all AEs and SAEs in the eCRF from the initial IMP dose through the completion of the follow-up telephone call.

Report all SAEs on an SAE Report Form to Mallinckrodt Pharmacovigilance.

Report all pregnancies to Mallinckrodt Pharmacovigilance on the Pregnancy Surveillance Form.

Submit the Safety Alert from Mallinckrodt to the IRB/IEC. (Submit any Expedited Safety Report or Suspected Unexpected Serious Adverse Reaction from Global Pharmacovigilance to the IRB/IEC.)

The reporting requirements for AEs are summarized in [Table 5](#).

Table 5: Reporting Requirements for Adverse Events

Seriousness	Reporting Time	Type of Report
All Serious	Within 24 hours of first knowledge of event	Initial report on the SAE Form, appropriate eCRF, and source document
	Within 24 hours of receipt of follow-up information	Follow up report on the SAE Form, appropriate eCRF, and source document
Nonserious	Per case report form submission procedure	Appropriate eCRF and source document

AEs

AEs can be reported spontaneously or elicited during open-ended questioning (ie, "How have you been feeling since your last visit?"), examination, or evaluation of a subject. Signs and symptoms must be recorded using standard medical terminology.

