- The sponsor will submit safety reports to the US FDA. (The sponsor will ensure that any Expedited Safety Report or Suspected Unexpected Serious Adverse Reaction are submitted to the FDA and other regulatory agencies as appropriate).

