10.1. Adverse Events

An AE is any untoward or undesirable medical occurrence in a subject who is administered an IMP, which does not necessarily have to have a causal relationship with this treatment.

A TEAE is defined as an event that begins or worsens on or after the start of study drug through 30 days after the date of the last dose. The first dose of IMP at the open-label extension phase will be used as cutoff date, the TEAEs started before the cutoff date will be summarized in the double-blind treatment phase and the TEAEs started on or after the cutoff date will be summarized in the open-label extension phase; Subjects who did not continue into the open-label extension phase will be summarized in the double-blind treatment phase only.

If a subject experiences the same AE more than once with different severity, then the event with the highest severity level will be tabulated in “by severity” tables. If a subject experiences the same AE more than once with different relationship to study drug, then the event with the most related level will be tabulated in “by relationship” tables. Note that AEs with a missing severity will be considered as severe, and AEs with missing relationship will be considered as related to study drug. Adverse events are considered treatment-related if the relationship to study drug is possibly related, related or missing.

The incidence of AEs will be summarized in tables with the number and percentage of subjects with AEs by SOC and PT. At each level of SOC or PT, a subject with multiple events will only be counted once per SOC or PT. Percentages of subjects with AEs will be calculated out of the number of subjects in the safety population. SOC will be presented alphabetically and PTs within each SOC will be presented in decreasing order of frequency based on the total number of subjects with each AE in the Acthar group. The following categories of TEAE will be summarized by SOC and PT by treatment group and total for the double-blind treatment phase and the open-label extension phase separately:

- TEAEs
- TEAEs by severity (Mild, Moderate, and Severe)
- TEAEs by relationship (Not Related, Unlikely Related, Possibly Related, and Related)
- Treatment related TEAEs
- Serious TEAEs
- Serious TEAEs by relationship (Not Related, Unlikely Related, Possibly Related, and Related)
- TEAEs leading to study drug discontinuation
- TEAEs leading to death

Overview tables of the above categories will also be provided.

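### Table 3 has no related grade for a truly novel reaction, so such an event can be left out of the treatment-related TEAE table (minor effect)

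*Protocol*

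**What the plan says.** Protocol 16.3 asks investigators to grade every AE and SAE with the four categories of Table 3.

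- **Possibly Related**: plausible timing after dosing "and follows a known response pattern to the suspected study treatment". The subject's condition or other therapy may also explain the event.
- **Related**: the same two conditions in the same words, plus confirmation by re-challenge or laboratory data.
- **Unlikely Related**: "The current state of knowledge indicates that a relationship is unlikely".
- **Not Related**: "No relationship between the experience and the administration of study treatment", with the event put down to other causes.

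Neither document defines a known response pattern, and neither gives a footnote or exception for a reaction without one.

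Three other provisions bear on the point. Protocol 16.2 explains that anticipated events are not expedited as single cases because it cannot be determined that "there is a reasonable possibility that the drug caused the event". The same section defines an unexpected AE as one "the nature and severity of which is not consistent with the applicable product information". Protocol 16.4 has the site pass on any "Suspected Unexpected Serious Adverse Reaction from Global Pharmacovigilance to the IRB/IEC" and has the sponsor ensure that "any Expedited Safety Report or Suspected Unexpected Serious Adverse Reaction are submitted to the FDA".

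On the analysis side, SAP 10.1 states: "Adverse events are considered treatment-related if the relationship to study drug is possibly related, related or missing". It lists eight TEAE categories, summarized separately for the double-blind and open-label phases, with overview tables of the same categories.

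**The concern.** Causality grading should be able to pick up harms that nobody yet associates with the drug. A scale that admits an event to a related grade only when the pattern is already known cannot do that for a new one. To call such a reaction related, an investigator has to depart from the written definition.

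The grade feeds the analysis. Relationship is named, with incidence and severity, as a basis for the safety evaluation (Protocol 14, SAP 3.2.3). Protocol 15.4.1 plans AE summaries by causality, and SAP 10.1 turns the grade into a treatment-related table. What is at stake is whether a reader of that table would see a truly novel reaction.

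**Working it through.** The plan states no figure on this point. The check applies the definitions as a decision rule and then follows the result through the SAP.

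**Step 1. Grade a novel reaction with plausible timing and no known pattern, using Table 3 as written.**

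| Grade | What it needs | Does the reaction fit? |
|---|---|---|
| Related | timing, known pattern, and re-challenge or laboratory support | No. It fails on pattern, even after a positive re-challenge |
| Possibly Related | timing and known pattern | No. It fails on pattern |
| Unlikely Related | knowledge that points against a relationship | Not cleanly. Having no known pattern is not the same as having evidence against a link |
| Not Related | no relationship, another cause | Not cleanly. Timing is plausible and no other cause is implied |

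The scale therefore has a gap, and no text tells the site how to fill it.

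**Step 2. Follow each possible site decision through SAP 10.1.**

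| Site decision | Counted as treatment-related? |
|---|---|
| Departs from the definition and grades Possibly Related | Yes |
| Leaves the grade blank | Yes, because missing counts as related |
| Unlikely Related or Not Related | No |

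**Step 3. Count the tables affected when the third decision is taken.** The eight SAP categories are as follows (* marks those that use the grade): TEAEs; by severity; by relationship*; treatment related*; serious; serious by relationship*; leading to discontinuation; leading to death. Three use the grade and 8 − 3 = 5 do not. The SAP's cutoff date assigns each TEAE to one phase, so one event is counted in one phase only.

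- Non-serious event: missing from 1 category and under a non-related heading in 1, so 1 + 1 = 2 of 8 affected.
- Serious event: missing from 1 and under a non-related heading in 2, so 1 + 2 = 3 of 8 affected.

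The overview tables repeat the same categories.

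**Step 4. List what does not depend on the grade.** All AEs are listed, with TEAEs flagged (SAP 10.1). AEs and SAEs are recorded whatever the relationship, and SAEs go to the sponsor within 24 hours even if they appear unrelated (Protocol 16.4). Protocol 8.1 allows dose reduction, and 17.1 allows discontinuation of IMP, without a related grade.

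**Step 5. Frequency.** The documents give no rate for novel reactions and no misgrading rate, so no expected number of affected events can be computed.

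**The case against.** The strongest reply is that the drop-out depends on a site decision that Table 3 does not call for. A novel reaction with plausible timing does not meet the wording of Unlikely Related or Not Related, so nothing obliges a site to choose either. A blank grade keeps the event in the treatment-related table. This stands, and it limits the conclusion to what can happen. It does not close the gap, because an investigator who wants to record suspicion still has no grade whose definition allows it.

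A reader might go further and infer that Table 3 contradicts the protocol's own provisions for unexpected AEs and suspected unexpected serious adverse reactions. The documents do not support that. Unexpectedness is judged against the package insert by nature and severity, while known response pattern is a separate, undefined test. An unlisted or unusually severe event can still follow a corticosteroid-like pattern, which Protocol 6.4 gives as the drug's usual profile. It can then be both unexpected and Possibly Related, so those provisions can operate with Table 3 as it is.

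Nor does 16.2 lay down a general test for a suspected reaction. The reasonable-possibility phrase appears there only as the reason for not expediting anticipated events. It implies a standard with which Table 3 sits poorly, and no more than that.

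The reply that the consequence is small is also right. No efficacy analysis uses the grade, and the safety tables that carry most weight are all-causality.

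**Conclusion.** The point holds as a gap in a stated rule, with a minor effect, and is worth considering. For one truly novel reaction graded Unlikely Related or Not Related, at most 1 of 8 TEAE categories omits it and at most 2 show it under a non-related heading, in one phase, with the overview tables following suit.

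This rests on three assumptions: the investigator reads Table 3 literally, the reaction is novel rather than merely unlisted, and the site enters one of the two lower grades rather than leaving the field blank.

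Two stronger readings should be set aside. A reader might infer biased grading between arms, but Protocol 12.1.1 blinds investigators and subjects to assignment, so the double-blind grading gives no ground for it. A reader might also infer that serious novel events would go unreported, but reporting to the sponsor does not depend on the grade.

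**What to change.** Redefine Possibly Related in Table 3 as plausible timing with a reasonable possibility that the drug caused the event, whether or not the response pattern is known. The phrase already appears in Protocol 16.2. Related can stay as it is. A novel reaction with a positive re-challenge would still stop at Possibly Related, but that is enough for SAP 10.1 to count it as treatment-related.

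The cost is one definition and any matching data-entry instruction (the documents do not show one). The downside is some loss of discrimination. Dosing is twice weekly for up to 24 weeks per phase, so up to 2 × 24 = 48 doses, and timing will look plausible for many background events. Somewhat more of them may be graded possibly related, though the reasonable-possibility condition restrains this.

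The change helps only events not yet graded. SAP version 3.0, effective 02 February 2022, already reports 55 subjects randomized, so much of the grading may be complete.
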